17/10/2017

SPECTROPHON Glucometry Monitor Accuracy Study

NCT03359629

Authors:

**[name], [name],
[name], [name]**

1. Kiryat Carmel Hospital, Israel
2. Ariel University, Israel
3. Spectrophon LTD, Rehovot, Israel
4. Maale HaCarmel Mental Health Center, Israel

Protocol date: 21/05/2017, ver. 2

-2017 -

Study Design

This study will examine the accuracy of Spectrophon NIGM incorporated in smart watches that noninvasively and indirectly detect the level of glucose in human blood. Adult subjects (n=200; both healthy individuals and participants with diabetes) will be recruited for the study in Maale Carmel Mental Health Center (MCMHC). In parallel to glucose measurements with NIGM, blood will be collected and the glucose level will be checked. An intravenous cannula (Venflon) will be inserted in cubital vein and blood will be collected twice in the beginning and at the end of the procedure and checked for glucose level with YSI 2300 Glucose Analyzer.

The measurements will be performed twice: before meal (subject should be in fasting state) and after meal with one-hour interval between two measurements.

The results of the measurements of the spectrometer biosensor will be compared to the results obtained from the YSI 2300 Laboratory Glucose Analyzer.

Inclusion criteria (for the group of healthy participants):

Healthy individuals between ages 18 and 75 that do not have diabetes and are able to sign informed consent form.

Exclusion criteria (for the group of healthy participants):

Hepatitis or HIV, tuberculosis, diabetes, hemophilia and other serious coagulation disorders, significant impaired venous access, pregnancy.

Inclusion criteria (for the group of participants with diabetes):

Clinical diagnosis of diabetes (I type, II type), age: 18-75, able to sign

informed consent form.

Exclusion criteria (for the group of participants with diabetes):

hepatitis or HIV, tuberculosis, hemophilia and other severe coagulation disorders, significantly impaired venous access, pregnancy.

Procedure

In the beginning of the experiment a participant must be in fasting state.

A blood sample is collected and checked for the glucose level with the reference devices YSI 2300 Glucose Analyzer.

NIGM is applied to the participant's skin after taking blood sample.

NIGM non-invasively measures glucose level in triplicate samplings.

After blood sampling, the participant receives food (no limitations to food type and quantity).

60 min. after meal, the second blood sample is collected and checked for the glucose level. NIGM is applied again to participant's skin after taking blood sample. NIGM non-invasively measures glucose level in triplicate samplings.

The application automatically saves every measurement into archive. To better control the process, the manual fixation of data obtained by NIGM is performed.

Statistical analysis

Mean absolute relative difference between Spectrophon NIGM, YSI 2300 Laboratory Glucose Analyzer and Accu-Chek Performa NC will be estimated for every sample to control the accuracy of the obtained data.

Regression analysis tools will be used to estimate the accuracy of NIGM measurements.

Principal investigator

[name]

[name]
המחלקה לפסיכיאטריה
טכניון
המרכז הרפואי לבראיות הנפש
שירות הכרמל

Signature

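### Does the two-sentence analysis plan need rules for the six clustered NIGM readings per subject?

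*Combined protocol and SAP*

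**What the plan says.** Study Design sets the numbers: "Adult subjects (n=200; both healthy individuals and participants with diabetes) will be recruited", and "The measurements will be performed twice: before meal (subject should be in fasting state) and after meal with one-hour interval between two measurements".

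Procedure describes one blood draw followed by NIGM readings at the fasting occasion: "NIGM non-invasively measures glucose level in triplicate samplings". An hour after the meal the pattern repeats: "the second blood sample is collected and checked for the glucose level", then a second triplicate. Study Design's phrase that "blood will be collected twice in the beginning and at the end of the procedure" could be misread as two draws each time, but Procedure describes a single draw per occasion.

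Procedure also states that "The application automatically saves every measurement into archive".

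The Statistical analysis section has two sentences. The first says that MARD among the devices "will be estimated for every sample to control the accuracy of the obtained data". The second reads "Regression analysis tools will be used to estimate the accuracy of NIGM measurements". The section promises no confidence interval, standard error, hypothesis test or accuracy threshold.

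**The concern.** Accuracy is the purpose of the study, and MARD and regression are the only analyses named. The data are nested: readings within a triplicate, triplicates within a person. Some positive correlation within a triplicate is likely, because the three differences share one YSI value and any error in that value is common to all three. Glucose drift since the draw and sensor placement may be shared as well.

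Two consequences looked possible. First, regression software prints standard errors by default. Run on 1,200 rows as if independent, it would overstate precision without anyone having chosen to do so. Second, the plan names a unit for MARD but does not define it. Procedure uses the word sample for the blood draw and a related word for the NIGM readings. The blood sample is the likelier meaning, but even then the plan does not say whether three absolute relative differences are averaged or the three NIGM values are averaged first. Those choices give different MARDs, and the choice could be made after the data are seen.

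**Working it through.** **Counts, from Study Design and Procedure.** 200 subjects × 2 occasions = 400 YSI values; 400 × 3 = 1,200 NIGM readings. The plan gives no derivation of n = 200 and no interval, so there is no precision figure of its own to reproduce.

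**Assumed inputs.** The documents give no correlations. Let r1 be the error correlation within a triplicate and r2 that between a subject's two occasions. Both are shown over a range.

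**Point estimates.** Every subject contributes six readings, so the average of 1,200 absolute relative differences equals the average of 400 triplicate averages of those differences. Clustering leaves this MARD unchanged. It does not bias the mean difference or the least-squares slope either.

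**Mean bias, if a default 95% interval were computed.**

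- On 1,200 rows, each reading correlates with 2 others at r1 and 3 at r2: design effect = 1 + 2·r1 + 3·r2.
- On 400 triplicate means with subject ignored: design effect = 1 + 3·r2/(1 + 2·r1).
- Coverage = 2Φ(1.96/√design effect) − 1.

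| r1, r2 | 1,200 rows: design effect | coverage | 400 rows: design effect | coverage |
|---|---|---|---|---|
| 0.1, 0 | 1.2 | 93% | 1.00 | 95% |
| 0.2, 0.1 | 1.7 | 87% | 1.21 | 92% |
| 0.5, 0.1 | 2.3 | 80% | 1.15 | 93% |
| 0.5, 0.5 | 3.5 | 70% | 1.75 | 86% |
| 0.7, 0.3 | 3.3 | 72% | 1.38 | 90% |
| 0.9, 0.5 | 4.3 | 66% | 1.54 | 89% |

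At (0.9, 0.5) the true standard error is √4.3 = 2.07 times the default on 1,200 rows.

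**Slope.** YSI is constant within a triplicate, so with constant error variance and r2 = 0 the design effect is 1 + 2·r1. Coverage is 93% at r1 = 0.1, 88% at 0.3, 83% at 0.5 and 76% at 0.9. These figures depend on the error model. I simulated the slope under assumed glucose values in mg/dL: half the subjects diabetic; fasting 92 (SD 9) healthy and 140 (SD 35) diabetic; post-meal rise 30 (SD 18) and 60 (SD 30). With error proportional to glucose, default coverage is about 85% with no correlation at all and about 66–68% at (0.5, 0.1), against 82% at (0.5, 0.1) with constant error. Unequal variance is therefore a separate cause. Subject-clustered standard errors gave about 94% in both models at (0.5, 0.1).

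**Averaging NIGM first.** With normal relative error, the mean of three has SD √((1 + 2·r1)/3) times that of one reading. With zero mean error, MARD scales by the same factor; with a mean error of one error SD, the ratio comes from the mean of the folded normal.

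| r1 | ratio, no bias | ratio, bias of one error SD |
|---|---|---|
| 0.1 | 0.63 | 0.88 |
| 0.3 | 0.73 | 0.91 |
| 0.5 | 0.82 | 0.93 |
| 0.7 | 0.89 | 0.96 |
| 0.9 | 0.97 | 0.99 |

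With a bias of two error SDs the ratio is 0.99 or more throughout.

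**What the plan commits to.** The coverage figures describe intervals that the Statistical analysis section does not say will be computed. Nothing in it says the rows are treated as independent: a regression on triplicate means, or a mixed model, fits its wording equally well.

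**The case for a change.** The strongest case for a change is that the two gaps cover each other's weak end. When r1 is high, default precision on unaveraged rows is badly overstated. When r1 is low and the device is nearly unbiased, precision suffers little but the averaging rule moves MARD most, to 63% of the single-reading value at r1 = 0.1. So for a device with small bias, one or the other matters at any r1. The remedy is a few sentences of analysis wording, and archived readings should allow either calculation, provided they can be linked to subject and occasion, which the protocol does not state.

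Most of this stands as description. The nesting is real, positive correlation is likely, and the MARD unit is loose. It does not show that a planned result is wrong. The precision argument needs an interval or test that the plan does not promise, computed in a way that it does not specify. The averaging argument concerns which of two legitimate quantities is reported: the error of a single reading or the error of a triplicate mean. Each is a valid description of the device so long as the report says which it is. With no acceptance limit, the choice cannot turn a failure into a pass.

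**Conclusion.** No change to the plan is called for. The plan omits detail on the unit of analysis and on repeated readings, but it states nothing incorrect. The per-reading MARD, mean bias and slope estimates hold under clustering, and no interval, test or threshold depends on an independence assumption.

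The possible effect runs from negligible to large, and the documents cannot settle where it falls. Default coverage for mean bias on 1,200 rows would be 93% at (0.1, 0) and 66% at (0.9, 0.5); on triplicate means, 95% to 86% over the settings shown. Averaging first would put MARD at 63–97% of the single-reading value with no bias and 88–99% with a bias of one error SD, for r1 from 0.1 to 0.9. All of this rests on assumed correlations and normal errors; the simulated slope figures also rest on the assumed glucose distribution.

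An analyst would ordinarily label MARD as single-reading or triplicate-mean and, if precision is reported, treat the subject as the independent unit. Writing that down beforehand would be an optional clarification.

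### Each single YSI draw precedes the NIGM triplicate with no lag limit and no required draw time, so glucose change over the lag enters the NIGM-YSI difference; probably small, cheap to prevent

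*Combined protocol and SAP*

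**What the plan says.** The Procedure gives the same order twice. Fasting: one blood sample is taken for the YSI analyser, then "NIGM is applied to the participant's skin after taking blood sample". Post-meal: "60 min. after meal, the second blood sample is collected and checked for the glucose level", and then "NIGM is applied again to participant's skin after taking blood sample". On each occasion, "NIGM non-invasively measures glucose level in triplicate samplings". The meal between the two sessions is unrestricted in type and amount.

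Study Design says "An intravenous cannula (Venflon) will be inserted in cubital vein and blood will be collected twice in the beginning and at the end". Read with the Procedure, where the post-meal sample is called the second, this means two draws in total, one per session. It does not mean a draw on each side of a triplicate. Study Design also says that blood is taken in parallel with the NIGM measurement, without saying how close in time the two must be.

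The recording provisions concern the device only: "The application automatically saves every measurement into archive", and "To better control the process, the manual fixation of data obtained by NIGM is performed". The Procedure gives no maximum draw-to-reading interval, no spacing or duration for the triplicate, and no requirement to note the time of a draw. Statistical analysis names MARD and regression, with no time matching and no lag adjustment.

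**The concern.** The purpose of the study is agreement between the watch and the YSI analyser, so the timing of each pair is part of the measurement. The stated order puts every device reading later than its reference. Averaging the triplicate does not remove this, because all three readings fall on the same side of the draw.

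If glucose is steady, nothing is lost. If it is moving, as it may be an hour after a meal, the change over the lag is added to the device's own error. With one reference value per session the rate of change is not measured, so the drift cannot be subtracted later. Without a draw time, nobody can show afterwards that the lag was short.

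**Working it through.** **Inputs from the protocol.** n = 200; two sessions per person; one YSI draw per session, hence 200 × 2 = 400 reference values. The protocol gives no lag, rate of change, glucose level, expected MARD or accuracy threshold, so it has no figure to reproduce.

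**Assumptions.** Reference glucose 150 mg/dL; rate 0.5, 1 or 2 mg/dL/min, common to all participants; lag 2 or 5 min; true MARD 10%; normal, unbiased device error; one device value per person and session; no drift when fasting; no sensor delay.

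**Step 1, drift.** d = 100 × rate × lag / 150, in percent of the reference.

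**Step 2, device error.** For a normal error with mean 0, MARD = SD × √(2/π), so SD = 10 × √(π/2) = 12.53%.

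**Step 3, post-meal MARD with drift.** This is the mean of |N(d, SD)|, which equals SD × √(2/π) × exp(−d²/(2 SD²)) + d × [1 − 2Φ(−d/SD)]. At d = 6.67% it is 10 × 0.868 + 6.67 × 0.405 = 11.38%.

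**Step 4, both sessions.** The average of the step 3 value and the fasting 10%.

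| Rate (mg/dL/min) | Lag (min) | d (%) | Post-meal MARD (%) | Both sessions (%) |
|---|---|---|---|---|
| 0.5 | 2 | 0.67 | 10.01 | 10.01 |
| 0.5 | 5 | 1.67 | 10.09 | 10.04 |
| 1 | 2 | 1.33 | 10.06 | 10.03 |
| 1 | 5 | 3.33 | 10.35 | 10.18 |
| 2 | 2 | 2.67 | 10.23 | 10.11 |
| 2 | 5 | 6.67 | 11.38 | 10.69 |

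**Step 5, sampling error for scale.** The variance of the absolute error is 12.53² − 10² = 57.1. The 95% half-width is 1.96 × √(57.1/200) = 1.05 points for one session and 1.96 × √(57.1/400) = 0.74 points for 400 independent pairs. It is wider if a person's two pairs are positively correlated. All six two-session shifts (at most 0.69) lie inside 0.74. For the post-meal session alone, only the last row's shift (1.38) exceeds 1.05.

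**Step 6, direction.** With the same SD and a device bias of −5%, MARD is 10.79% without drift and 10.09% with a drift of +6.67%. The lag can therefore flatter a biased device as well as penalise an unbiased one.

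**Step 7, sensor delay.** If the signal simply trails blood glucose by τ minutes, the effective lag is the draw-to-reading lag minus τ. Reading somewhat after the draw would then bring the pair closer together. The documents give no response time.

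**The case against.** The strongest reply is that Study Design already intends the two measurements to be contemporaneous, and that a reading within a minute or so makes the matter negligible: at 1 min and 1 to 2 mg/dL/min, post-meal MARD is 10.01% to 10.06%. The protocol specifies no separate post-meal analysis, so the two-session figures are the fairer headline, and they lie within sampling error. The rates are assumptions, and in some participants, healthy ones included, glucose may hardly be moving. All of this stands. It limits the size of the point but does not supply a tolerance or a draw time.

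A reader might infer that, because the lag is not capped, it could be 10 minutes, which under the same assumptions gives a post-meal MARD of 11.4% (1 mg/dL/min) to 15.2% (2 mg/dL/min). Nothing in the documents indicates such a lag, and it fits poorly with measurements described as parallel. A reader might also infer that the design is biased against the device. Steps 6 and 7 show that the direction is not fixed. Nor do the documents show that draw times will go unrecorded, only that recording them is not required.

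The regression is more exposed than MARD, because it uses signed differences. The 95% half-width of a mean post-meal signed difference is 1.96 × 12.53/√200 = 1.74 points, which three of the six drifts in the table exceed. That needs a drift in one direction across participants, and mixed directions would partly cancel. It does not establish a material bias.

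The Accu-Chek meter named in Statistical analysis might give another value close to the NIGM readings, but the Procedure never says when it is used.

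**Conclusion.** The gap is real and minor. The Procedure fixes the order as draw then device at both time points, sets no maximum lag and requires no draw time. Glucose change over the lag therefore becomes part of the NIGM-YSI difference and cannot be removed afterwards.

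Its size cannot be derived from the documents. Under the stated assumptions it adds 0.01 to 1.4 points to a post-meal MARD of 10%, and at most about 0.7 points over both sessions. With a true MARD of 20% it matters less still: the most extreme of the six cases gives 20.70% post-meal. These figures rest on the assumed rates, lags, glucose level and true MARD, a common drift, and no sensor delay. No stated threshold or conclusion is shown to change. The case for acting is that the lag is avoidable at almost no cost and cannot be reconstructed if it is not recorded.

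**What to change.** In the Procedure, at both time points:

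- have the sensor in place before the draw and start the triplicate at the draw;
- record the clock time of each draw and of each NIGM reading;
- state a short maximum draw-to-reading interval, justified from the duration of the triplicate.

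In Statistical analysis, pre-specify a sensitivity analysis that excludes pairs outside that interval, reported by time point. Recorded times allow exclusion or an analysis by lag. They do not allow the drift to be subtracted.

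Drawing the reference sample during the triplicate, so that readings fall on both sides of it, is optional and suitable only if it does not disturb the reading. The documents do not say how long the triplicate lasts or which arm is used. If the sensor is known to trail blood glucose, the protocol should say so and set the interval accordingly; recording the times is useful either way.

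Cost: a minor reordering of steps, one extra time entry per draw (and one per NIGM reading if the application does not already store it), and a few pairs excluded in the sensitivity analysis. No extra blood, cannula or visit is needed.

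### Nothing keeps the YSI result from whoever applies and records NIGM, and the plan does not fix which NIGM readings enter the MARD, so a bias in the device's favour is possible

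*Combined protocol and SAP*

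**What the plan says.** The Procedure section of the combined protocol and SAP gives this order for the fasting occasion: "A blood sample is collected and checked for the glucose level with the reference devices YSI 2300 Glucose Analyzer". The next step reads "NIGM is applied to the participant's skin after taking blood sample", followed by "NIGM non-invasively measures glucose level in triplicate samplings". The post-meal occasion repeats the pattern: "60 min. after meal, the second blood sample is collected and checked for the glucose level", then "NIGM is applied again to participant's skin after taking blood sample", again in triplicate.

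The Study Design section describes the timing more loosely: "In parallel to glucose measurements with NIGM, blood will be collected and the glucose level will be checked".

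On recording, the Procedure states "The application automatically saves every measurement into archive". It adds that, to control the process better, "the manual fixation of data obtained by NIGM is performed".

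The Statistical analysis section says that MARD between NIGM, the YSI and a third meter will be estimated sample by sample, and that regression will be used. It does not define a sample. It does not name the archive or the hand record as the source of NIGM values, and it does not say how three readings become one comparison. No section mentions masking, failed readings or repeated readings.

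**The concern.** Agreement with the YSI is the central question of this study. An accuracy comparison is protected when the test reading is fixed before anyone handling the test device can see the reference value. Here the listed order permits the reverse.

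That each number is generated by a machine protects the number. It does not protect the decisions around it: whether to re-apply the watch when a reading looks odd beside the YSI value, and which readings to carry forward. An operator could make such decisions in good faith. If they lean towards the reference, MARD falls and the regression agreement improves although the device is no more accurate. Unlike sampling error, this shift always favours the device and does not shrink with more participants.

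The device company appears among the author affiliations, so rules fixed in advance would also protect the result from later challenge.

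**Working it through.** The plan gives no figure for NIGM precision, no MARD target and no derivation of its sample size, so there is no planned figure to reproduce. The check has two parts.

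**1. What the text allows**

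- *Order.* The Procedure lists draw and check, then NIGM. The phrase that places NIGM afterwards refers to taking the blood, not to the YSI result, and Study Design says the two run in parallel. Prior knowledge of the YSI value is therefore possible but not established.
- *Records.* The archive holds every measurement. The hand record is introduced as a control. No comparison of the two is specified, and neither is named as the analysed source.
- *Readings.* Three per occasion are prescribed. Repeats are neither provided for nor ruled out, and scoring of the triplicate is undefined.

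**2. How large the effect could be**

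Input from the documents: 200 participants × 2 occasions = 400 occasions, with three readings each.

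Assumptions: relative error is normal with mean zero; true single-reading MARD is M = 20%; a share ρ of the error variance, 25% to 75%, is common to readings within an occasion.

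Model: error of a reading = b + w, with Var(b) = ρσ² and Var(w) = (1 − ρ)σ². Since MARD = σ√(2/π), σ = 0.20 / 0.7979 = 0.2507. Simulation of 400,000 occasions gives:

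| Rule | ρ = 0.25 | ρ = 0.50 | ρ = 0.75 |
|---|---|---|---|
| First three, each scored | 20.0% | 20.0% | 20.0% |
| Best 3 of 4, every occasion | 14.6% | 15.2% | 16.3% |
| Worst of the three dropped, every occasion | 13.6% | 14.2% | 15.5% |

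The model scales with M. Best 3 of 4 lowers MARD by (20 − 14.6)/20 = 27% down to (20 − 16.3)/20 ≈ 18%, whether the true value is 10%, 20% or 30%. With 90% of variance shared, best 3 of 4 gives 17.5%.

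*Occasional selection.* Best 3 of 4 at 10% of occasions shifts MARD by 0.10 × (20 − 14.6) = 0.54 points down to 0.10 × (20 − 16.3) = 0.37 points.

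*Sampling error of the three-reading average.* The SD per occasion is 0.092 at ρ = 0.25 and 0.125 at ρ = 0.75.

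- Two occasions per person treated as independent: 1.96 × 0.092/√400 = 0.9 points to 1.96 × 0.125/√400 = 1.2 points.
- Effectively one occasion per person: 1.96 × 0.092/√200 = 1.3 points to 1.96 × 0.125/√200 = 1.7 points.

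Best-3-of-4 selection would equal the sampling error if it happened at about 0.9/5.4 = 17% to 1.7/3.7 = 46% of occasions.

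*Scoring rule, with no selection at all.* Scoring the mean of three gives M√((1 + 2ρ)/3): 20 × √(1.5/3) = 14.1% at ρ = 0.25 and 20 × √(2.5/3) = 18.3% at ρ = 0.75, against 20% when each reading is scored. This is a different quantity rather than a bias, but the plan does not say which one will be reported.

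**The case against.** The strongest case against runs as follows. The documents never say that the operator sees the YSI value, and the parallel wording in Study Design suggests the two measurements may overlap. Triplicates are prescribed, and no repeat is provided for. Estimating MARD sample by sample leans against picking readings. The archive is automatic and complete, and the hand record is there as a control, so treating the archive as the source is the natural reading. The large figures assume selection at every occasion.

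Most of this stands, and it limits the point:

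- A reader might infer that the YSI result is known before NIGM is read. The text permits this but does not show it.
- A reader might infer that selection would leave no trace. The documents do not support that: every measurement is archived, so extra readings could be found by comparing the archive with the hand record. What is missing is any instruction to make that comparison.
- A reader might infer that company staff operate the watch. Nothing says so; recruitment is at the mental health centre.

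What does not stand is that the gaps are therefore harmless. Parallel timing is not a masking rule. A natural reading is not a stated source of record. Dropping one reading of the prescribed three needs no extra measurement.

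**Conclusion.** The point holds as a gap in protection, not as evidence that readings will be selected. The plan allows the reference to be known when NIGM is applied and recorded, does not name the analysed record, and does not define how the triplicate is scored.

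The downward direction applies only to choices made towards a known reference. Transcription errors made without that knowledge need not lower MARD.

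The size cannot be determined from the documents. Under the stated assumptions, selection at every occasion would take 3.7 to 5.4 points off a true MARD of 20%, well beyond sampling error. Selection at one occasion in ten would take off about 0.4 to 0.5 points, within it. The open scoring rule alone leaves 1.7 to 5.9 points (20 − 18.3 to 20 − 14.1) to be settled after the data are seen. All of these figures rest on the assumed normal errors, the 20% MARD and the 25–75% shared variance. The change is worth making because it costs very little.

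**What to change.** 1. *Procedure, both occasions:* complete the NIGM triplicate and save it to the archive before the YSI result is shown to the person applying and recording NIGM. The restriction covers only that person and does not affect who else sees the result.
2. *Statistical analysis, source:* take NIGM values only from the automatic archive export. Use the hand record as a check and list every mismatch.
3. *Statistical analysis, readings:* analyse the first three archived readings at each occasion, in order of recording. List any further readings or failures without substituting them. Compute MARD on each of the three readings separately, averaged within occasion, and report the MARD of the mean of three as secondary.

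The documents do not say that the archive stamps times, so confirm before the study starts that the export preserves the order of recording.

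Cost: a few sentences, with no extra participants, samples or staff. The operator sees the YSI value later, presumably by a few minutes, though the documents do not give the duration of a triplicate. The reported MARD may look slightly less favourable.

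### MARD is to be estimated with no interval, no performance goal and no reference point, so the figure alone cannot show whether NIGM adds information about glucose

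*Combined protocol and SAP*

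**What the plan says.** Study Design gives the aim: "This study will examine the accuracy of Spectrophon NIGM incorporated in smart watches". It sets the reference: the sensor results "will be compared to the results obtained from the YSI 2300 Laboratory Glucose Analyzer". It sets the size: "Adult subjects (n=200; both healthy individuals and participants with diabetes) will be recruited". No rationale for 200 and no split between the two groups is given. Each person is measured on two occasions: "The measurements will be performed twice: before meal (subject should be in fasting state) and after meal". On each occasion, according to Procedure, "NIGM non-invasively measures glucose level in triplicate samplings".

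The analysis plan is two sentences. The first names the metric and the devices, "Mean absolute relative difference between Spectrophon NIGM, YSI 2300 Laboratory Glucose Analyzer and Accu-Chek Performa NC", and says that it "will be estimated for every sample to control the accuracy of the obtained data". The second reads "Regression analysis tools will be used to estimate the accuracy of NIGM measurements".

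There is no hypothesis, MARD limit, confidence interval, regression model, criterion for slope or intercept, or rule for combining the three readings. Accu-Chek appears only in the MARD sentence. No step in Procedure measures it, and nothing makes it a standard that NIGM must meet.

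**The concern.** MARD has no built-in point at which a device shows no skill. Anyone who knows whether a person has diabetes and whether they have eaten can guess a typical glucose value and obtain a moderate MARD without a sensor. How good that guess is depends on the spread of glucose in each group and on the case mix, and the protocol fixes neither. Without a reference point the reader cannot tell whether a reported MARD reflects the sensor or the narrowness of the sample.

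Timing matters too. A limit chosen after the MARD is known can be one that the device meets, so it would not be a sound test. As written, no MARD value would count as a failure to show accuracy, although accuracy is the study's only aim.

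**Working it through.** **Figure to reproduce.** None. The 200 comes without alpha, power, SD, margin or target precision.

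**Inputs from the documents.** 200 people, two occasions each, so 400 reference values; three NIGM readings per occasion; two groups in unstated proportion.

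**Assumed inputs (not in the documents).** Log-normal glucose, mean in mg/dL (CV):

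| Set | Healthy fasting | Healthy post-meal | Diabetes fasting | Diabetes post-meal |
|---|---|---|---|---|
| Low | 90 (8%) | 110 (15%) | 130 (20%) | 165 (22%) |
| Mid | 92 (10%) | 120 (20%) | 145 (28%) | 195 (30%) |
| High | 95 (11%) | 130 (25%) | 160 (38%) | 220 (38%) |

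**Step 1: no-sensor MARD, simulated.** The prediction is one constant per group and meal state, chosen to minimise MARD (100,000 people per case):

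| Diabetes share | 10% | 25% | 50% | 75% |
|---|---|---|---|---|
| Low | 9.8 | 10.9 | 12.8 | 14.6 |
| Mid | 12.8 | 14.5 | 17.1 | 19.7 |
| High | 15.6 | 17.8 | 21.3 | 25.0 |

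Using the cell median instead raises these slightly: the overall range becomes 9.9 to 26.5, and the mid value at 50% becomes 17.7. A cruder guess, one constant for everybody, gives 13.7 to 31.8.

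**Step 2: by cell.** For small CV, no-sensor MARD is approximately sqrt(2/pi) x CV = 0.798 x CV.
- Healthy fasting: 0.798 x 8 = 6.4; x 10 = 8.0; x 11 = 8.8. So about 6-9%.
- Healthy post-meal: 0.798 x 15 = 12.0; x 20 = 16.0; x 25 = 19.9.
- Diabetes fasting: 0.798 x 20 = 16.0; x 28 = 22.3; x 38 = 30.3.
- Diabetes post-meal: 0.798 x 22 = 17.6; x 30 = 23.9; x 38 = 30.3.

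Check on the mid set at 50:50: (8.0 + 16.0 + 22.3 + 23.9)/4 = 17.6, against 17.1 (best constant) and 17.7 (median) by simulation.

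**Step 3: the same 15% against different floors (cell-median predictor).**
- Low spread, 25% diabetes: 15 - 11.1 = +3.9, worse than no sensor.
- Mid spread, 25% diabetes: 15 - 14.9 = +0.1, no different.
- High spread, 50% diabetes: 15 - 22.5 = -7.5, clearly better.

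**Step 4: why a pooled comparison is not enough.** Take a device at 15% in every cell, the mid set and a 50:50 mix. The cell differences are 15 - 8.0 = +7.0, 15 - 16.0 = -1.0, 15 - 22.3 = -7.3 and 15 - 23.9 = -8.9. A simulation with 200 people (assumed within-person correlation 0.6) put the pooled paired difference at -2.7 with half-width 2.2, so the upper limit is -2.7 + 2.2 = -0.5. The pooled comparison favours the device although its healthy fasting error is nearly twice that of guessing (15/8.0 = 1.9).

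**Step 5: precision available.** Half-width of pooled MARD = 1.96 x SD x sqrt((1 + rho)/2/200).
- SD 8, rho 0: 0.8 points. SD 20, rho 1: 2.8 points.
- With half-normal errors at MARD 15%, SD = 15 x sqrt(pi/2 - 1) = 11.3. A cell of 100 people gives 1.96 x 11.3/sqrt(100) = 2.2; a cell of 50 (25% of 200) gives 3.1; a cell of 20 (10% of 200) gives 5.0.

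For the pooled paired difference, an assumed half-width of 2.5 means SE = 2.5/1.96 = 1.28. The chance that the upper limit falls below zero is then about 65% at a true difference of -3.0 and 73% at -3.3.

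**The case against.** **An estimation study needs no pass/fail rule.** This stands in part. A descriptive accuracy study can be valid without a hypothesis, and the plan states no conclusion. A reader might infer that the plan would declare the device accurate at any MARD; the text says only that quantities will be estimated. But a descriptive MARD still needs an interval and something to be read against, and both are missing.

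**Accu-Chek is the benchmark.** It is named in the MARD sentence, so this deserves an answer. No criterion is attached and no measurement step is described, so it does not fill the gap. The regression sentence does not fill it either, since it has no model and no criterion.

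**The no-sensor floor is a reviewer's construct on assumed data.** The size is indeed assumed. The predictor is also demanding, because it uses the study's own YSI values together with known group and meal state. The remedy does not depend on the assumed distributions, because the benchmark would be computed from the trial's YSI values.

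**Precision may not suffice.** This stands. A 3-point pooled advantage would be shown only about two times in three, and cell results are less precise than pooled ones.

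**Conclusion.** The concern holds in this form: MARD is to be estimated without an interval, a performance goal set in advance or a reference point, so a raw MARD cannot show whether NIGM adds information. That part comes directly from the text.

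The size is conditional. With the three assumed spreads and 10-75% diabetes, a no-sensor prediction by group and meal state gives about 10-25%, about 17% at 50:50 with moderate spread, and about 6-9% in healthy fasting people. A 15% MARD can therefore fall on either side of no sensor.

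Three stronger readings are not supported:
- A reader might infer that guessing would reach the mid to high teens in this design. The documents fix neither spread nor case mix, so that is only one scenario.
- A reader might infer that reference values cluster tightly throughout. Under the assumptions, that fits healthy fasting people only; the diabetes cells run from about 16% to 31%.
- A reader might infer that any limit set later is bound to be one the device meets. It could be, which is reason enough to set it in advance, but nothing in the documents shows that it will be.

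**What to change.** Before data are seen, add to Statistical analysis:

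1. A stated rule that reduces the three NIGM readings to one absolute relative difference from YSI per participant and occasion, saying whether readings are averaged first or the three errors are averaged.
2. MARD with a 95% interval, bootstrapped by participant, overall and in each of the four group-by-meal-state cells.
3. In each cell, the MARD of a no-sensor prediction (median YSI of the other participants in that cell) and the paired difference, NIGM minus no-sensor, with its 95% interval.
4. A claim of useful measurement only for cells where the upper limit of that difference is below zero, and no such claim resting on the pooled difference alone.
5. If the sponsor intends to call the device accurate, the maximum MARD for that claim, stated in advance and judged by the upper 95% limit.

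The cost is a paragraph of text and a few lines of code on data already planned, with no extra participants, visits or samples. The downside is that the sponsor commits in advance to a result that the device can fail, and that precision within cells is lower than pooled, especially if one group is small.
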